Successful execution of this study will lay the groundwork for a clinical trial to compare the efficacy of a clot-specific imaging modality (**thrombus body scan or TBS**) that has the potential to be more accurate for the diagnosis of VTE, better able to establish the total clot burden in the body with a single test and more widely applicable to patients with renal failure and lung disease.

III. SUBJECT SELECTION

A total of eighty (80) subjects will be recruited for this study, which will be performed at the Massachusetts General Hospital (MGH). All eighty (80) subjects will be studied with the same protocol: a single injection of ⁶⁴Cu-FBP8 and PET-CT imaging at least three hours after injection at four bed positions, which will provide the imaging data for fresh blood clot at the three locations covering all three specific aims.

Inclusion Criteria:

Each subject must meet the following criteria to be enrolled in the study:

- 18 years of age or older with a clinically significant pulmonary embolus (PE) confirmed by a filling defect in CT angiography (CTA), and
- Subjects must receive the radiotracer injection within 72 hours of their diagnosis.

Exclusion Criteria:

- Subjects < 18 years of age
- Time of expected radiotracer injection > 72 hours from the time of a positive venous duplex ultrasound or CT-angiogram,
- Women subjects of childbearing potential who are pregnant, seeking to become pregnant, or have a positive serum pregnancy (beta-HCG) test,
- Unable to lie flat for 45 minutes as assessed by physical examination and medical history (e.g. back pain, arthritis, dyspnea),
- Weight that exceeds the PET camera table limit (300 kg)
- The subject will not be enrolled in the study if the radiation exposure for research studies during the prior 12 months, combined with the exposure from this study would exceed 50 mSv.
- Due to the radiation exposure from imaging studies, all women of childbearing potential will be required to have a negative serum pregnancy test performed prior to any imaging procedures on the same day (if not already done that day). Patients with a positive serum pregnancy test will be excluded. Breast feeding women will also be excluded.
- A pre-existing condition or use of a medication including vasopressors and tPA (due to its effects on clot) that in the opinion of the investigator may place the subject at a substantially increased risk
- Hemodynamic instability, including requiring escalating doses of vasopressor medication.

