
V. STUDY PROCEDURES

Subject Screening: Subjects will be studied while admitted in the hospital and followed up as an outpatient (via phone or after clinic follow up visit) for 1 year at 3, 6 and 12 months after their imaging. Additionally, subjects recently presenting to the MGH and / or admitted but discharged before enrolling into the study may return to MGH for the purpose of participating in this study. Initially, they will be screened only after the patient’s treating physician has ask the patient for permission to be contacted by the study staff. The screening will consist of an in-depth review of the medical records (notes, labs, imaging tests, medications, etc.) to ensure that the subjects meet the inclusion and exclusion criteria for the study. After the informed consent is obtained, a physician investigator will take a detailed history, perform a physical exam and assess the subject’s capacity to lie flat for imaging. Once inclusion criteria have been met and the subject consents to the study procedures, labs will be drawn daily (D-Dimer, PT, PTT, INR, platelets and fibrinogen) if not done so clinically for a maximum of 3 days from the day of initial CTA to the day of PET-CT.

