- For subjects admitted to the hospital close to the scheduled time for imaging, which is at least 3 hours after injection, the subject will be escorted (transported) in the wheelchair or stretcher/bed by hospital transport and/or study staff depending on the subject conditions to the PET-CT suite; we will follow the hospital standard procedures for patient transport. The PET-CT technician will submit a patient transport order through Epic. When the PET suite becomes available, the hospital transport team will transport to the PET-CT location. If the subjects need to be monitored during the transport, then one of the study physicians will be present during the transport.
- Subjects coming as outpatient will come to the hospital (Anesthesia or Pulmonary Research area) at least 4 hours prior to the imaging where they will be injected and monitored before taking them to the PET-CT imaging suite.
- Prior to the scan subjects will be asked to urinate to minimize the possibility that they will need to move during the scan.
- The subjects will be positioned on the scanner table; support devices under the back and/or legs will be used as needed to enable the patient to comfortably maintain his/her position throughout the scan.
- A scout image (Topogram) which takes about 10 seconds will be obtained to locate the proper fields for imaging.
- Afterwards, CT and PET scans will be obtained for four bed positions: thorax, pelvis and thighs (2 positions). The CT scan for each position of the PET scans is necessary to correct for the attenuation of the ⁶⁴Cu-FBP8 activity caused by body tissue. We will perform an additional PET/CT scan of the lower portion of the thighs in order to image the full/whole thighs to the knees. Consequently, a total of 4 CT and 4 PET scans will be performed in four different positions. Imaging duration will be less than 10 seconds for each CT, and 10 minutes for each PET scan. The total time of imaging is expected to be approximately 45 minutes.
- We may have to repeat a PET-CT scan if we have an unexpected problem (for example, if subjects need to change position during a scan).
- Subjects will be monitored throughout the imaging session, and measurements including heart rate, blood pressure, and pulse oximetry will be recorded.

Post-scan procedures:

- After the scans are completed and last vital signs collected, the subject will be escorted back to his/her room on the ward if applicable

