Radiation exposure has been assessed for ^{64}Cu -FBP8 using human time-activity curves extrapolated from the time-dependent rat biodistribution data. The cumulative activity (Bq-h/Bq) for each source organ was determined by integrating the area under the time-activity curves by using the least-squares analysis, and organ absorbed doses were estimated by using the software program OLINDA/EXM (version 1.0, Vanderbilt University, 2003). Based on these data, the kidneys are the primary critical organs, followed by urinary bladder and liver. The estimated effective dose for humans was 0.017 mSv/MBq.²³ Initial data in human volunteers confirmed this effective dose estimate. We plan to inject no more than 370 MBq (=10 millicuries) per subject, which would cause a maximal effective dose of approximately 6.2 milliSieverts (mSv), and is less than the proposed up to 15 mCi in the original IND. The radiation exposure in this study will be small and there is no evidence that it represents a major health risk. If subjects have participated in other research studies in the past 12 months that have involved radiation exposure, they will be asked to inform the investigators or study staff (by placing a check mark on the consent form verifying that they have or have not been exposed to other radiation in the past 12 months). If it is determined that the prior radiation exposure exceeds our current guidelines (i.e. 50 mSv/year) the subject will not be enrolled in this study. We estimate that the total exposure of each subject to ionizing radiation includes:

1. Topogram 0.5 mSv (for identifying scanning region for CT)
2. Low-Resolution CT scans in four positions (thorax, pelvis and thigh x2): 0.95 mSv x 4 (for attenuation-correction of PET), which 3.8 mSv.
3. ^{64}Cu -FBP8 Injection (10 mCi x 0.62 mSv/mCi): 6.2 mSv

The estimated total radiation dose for a subject is 10.5 mSv. However, if we repeat a PET-CT scan for an unexpected problem (for example, if subjects need to change position during a scan), the total radiation dose for will be 11.45 mSv.

Discomfort

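### Section VII tests prior radiation alone against 50 mSv and leaves out this study's 10.5 to 11.45 mSv, which the Section III exclusion criterion counts

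*Combined protocol and SAP*

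**What the plan says.** Two sections give a radiation rule for enrolment, both with the figure 50 mSv.

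- **Section III, Exclusion Criteria.** A subject is not enrolled if "radiation exposure for research studies during the prior 12 months, combined with the exposure from this study would exceed 50 mSv". The quantity tested is prior research exposure plus this study's dose.
- **Section VII, Radiation.** Subjects report earlier research radiation by a check mark on the consent form. The next sentence says that if the "prior radiation exposure exceeds our current guidelines (i.e. 50 mSv/year) the subject will not be enrolled in this study". The quantity tested is prior exposure only.

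Section VII then itemises this study's dose and totals it at 10.5 mSv. For the case where a scan has to be repeated, it says "the total radiation dose for will be 11.45 mSv". Section V (PET-CT imaging) allows for that case: "We may have to repeat a PET-CT scan if we have an unexpected problem". Neither enrolment rule says which of the two study doses is to be added.

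Section V (Subject Screening) describes a record review "to ensure that the subjects meet the inclusion and exclusion criteria for the study", and the Study Events table lists an eligibility checklist.

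**The concern.** The two sentences share a threshold and a consequence but compare different quantities with the threshold. Nothing in the protocol reconciles them.

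The location of the incomplete sentence matters. Section VII is the only place that describes a specific way of learning about earlier research radiation, and the sentence directly after it reads as the decision rule for that information. Staff acting on a ticked box could reasonably use it and not exclude someone whom Section III excludes.

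There is also a smaller gap in Section III itself. It does not say whether the study exposure to add is the planned dose or the dose with a repeat. If staff add the planned dose, a subject at the cut-off who then needs the permitted repeat ends above 50 mSv.

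What is at stake is a safety limit that the protocol sets for itself. Sample size, endpoints and analyses are untouched.

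**Working it through.** **Inputs, all from Section VII (Radiation):** topogram 0.5 mSv; attenuation-correction CT 0.95 mSv at each of four positions; tracer 10 mCi at 0.62 mSv/mCi; limit 50 mSv.

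**Step 1. Reproduce the protocol's study dose.**

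- As planned: 0.5 + 4 × 0.95 + 10 × 0.62 = 0.5 + 3.8 + 6.2 = 10.5 mSv.
- With one further CT position: 10.5 + 0.95 = 11.45 mSv.

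Both agree with the stated figures. As a cross-check, Section VII also gives 0.017 mSv/MBq and a maximum of 370 MBq, so 0.017 × 370 = 6.29 mSv against the stated 6.2 mSv. Since 10 mCi is 370 MBq, 0.62 mSv/mCi is 0.62 / 37 ≈ 0.0168 mSv/MBq. The difference is rounding.

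**Step 2. Highest prior exposure each rule admits.** Let P be prior 12-month research exposure and D the study dose.

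- Section III: P + D ≤ 50, so P ≤ 50 − D.
- Section VII sentence alone: P ≤ 50.

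| Study dose D (mSv) | Highest P, Section III | Highest P, Section VII alone | Highest total, Section VII alone | Excess over 50 |
|---|---|---|---|---|
| 10.5 (planned) | 50 − 10.5 = 39.5 | 50 | 50 + 10.5 = 60.5 | 10.5 / 50 = 21.0% |
| 11.45 (one repeat) | 50 − 11.45 = 38.55 | 50 | 50 + 11.45 = 61.45 | 11.45 / 50 = 22.9% |

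The rules disagree for P above 39.5 mSv (or 38.55 mSv) and up to 50 mSv.

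**Step 3. Section III applied with the planned dose, followed by a repeat.** A subject at the cut-off P = 39.5 mSv reaches 39.5 + 11.45 = 50.95 mSv, which is 0.95 mSv over the limit. This can happen only for P above 38.55 and up to 39.5 mSv.

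Step 2 takes prior exposure in Section VII to mean research exposure, as its context suggests. The sentence itself does not say so.

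**The case against.** The best defence is that Section III is the formal criterion, is correct, and is the stricter of the two. Section VII is risk narrative. Its sentence gives one sufficient ground for exclusion and never says that a subject at or below 50 mSv may enrol. Anyone with more than 50 mSv of prior research exposure also fails Section III, so both sentences can be obeyed, and obeying both gives the Section III result. On this view the totals of 60.5 and 61.45 mSv describe a protocol deviation, not something the protocol permits. This stands as to weight: the sentence is incomplete and does not override Section III. It does not remove the need for a correction, because the incomplete rule is the one attached to the consent-form check mark.

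On the repeat scan, the defence is that exposure from this study naturally includes a repeat, that both totals are printed in Section VII, and that the affected window is only 0.95 mSv wide. The size is indeed small. But Section III does not say which total to use, and the answer has to be fixed before anyone knows whether a repeat will be needed.

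A third objection is that a hard-coded cut-off is falsely precise. With 6.29 mSv for the tracer, the total with one repeat would be 10.5 + 0.95 + 0.09 = 11.54 mSv and the cut-off 50 − 11.54 = 38.46 mSv. The protocol also sets no maximum number of repeats. The first point is rounding. The second is fair: 11.45 mSv covers one repeat and no more.

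Finally, the content of the checklist is not in the documents, so it may already carry the combined rule. If it does, that part of the change reduces to confirming the dose figure.

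**Conclusion.** The concern holds. The Section VII sentence leaves this study's dose out of a limit that, under Section III, includes it. The sections give different answers for prior research exposure above 39.5 mSv (38.55 mSv counting one repeat) and up to 50 mSv. The 21.0% to 22.9% overshoot arises only if staff rely on Section VII without Section III. The 50.95 mSv total arises only if Section III is applied with the planned dose and a repeat follows.

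The documents give no frequency of prior research exposure in this range; I assume few subjects are affected. This is a minor inconsistency that should be corrected because it concerns subject protection.

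**What to change.** Replace the Section VII sentence with the combined rule, and use the same wording in Section III and on the eligibility checklist: do not enrol a subject if research radiation exposure in the prior 12 months plus 11.45 mSv (this study's dose, including one repeat scan) would exceed 50 mSv, that is, if prior research exposure is above 38.55 mSv.

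This costs one changed sentence in Section VII and one dose figure added to Section III and the checklist. The cut-off becomes 39.5 − 38.55 = 0.95 mSv stricter than one based on the planned dose, which should exclude at most a few additional subjects.
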